## **17.5. COAGULATION PARAMETERS**

For coagulation parameters, values and changes from baseline will be tabulated by treatment group and assessment time.

Scatter plots highlighting individual results for coagulation parameters (prothrombin time/INR, activated partial thromboplastin time and thrombin clotting time) before and after study treatment administration (last value) will be produced.

## **17.6. ECG**

Individual tabulated data for ECG abnormalities will be displayed.

## **17.7. PHYSICAL EXAMINATION**

Descriptive statistics over time of body weight values and changes from baseline will be tabulated by treatment group and assessment time.

The results on global physical examination will never be tabulated because it's only used to detect potential AE. They will be only listed in appendix 16 of the ICH report.

## 17.8. CONCOMITANT MEDICATIONS

Concomitant medications will be tabulated by treatment group and according to the first study drug intake and V9 (Taken at least once before first study drug administration, taken at least once after first-study drug administration and not started at V9, started at V9) within a descriptive perspective. They will be classified by therapeutic area according to the WHO-DRUG dictionary using the "anatomical therapeutic chemical" classification on the safety set.

Note: a concomitant medication which begins before first study drug administration and is on-going after first study drug administration, is counted in both periods "Taken at least once before first study drug administration" and "taken at least once after first-study drug administration and not started at V9".

## 18. CHANGES SINCE PROTOCOL REDACTION

The following modifications were made to statistical analyses compared to those envisaged in the Version 9 of the protocol dated December 6th, 2016:

- predictive probability of success and conditional power for primary efficacy criterion will be added
- subgroups analyses for primary criterion will be added
- ROC curves for primary criterion exploratory analyses according to DHA will be added
- the secondary criteria analyses repeated on the PP set will not be performed
- the secondary criteria were extended to the flutter detection as the primary efficacy criterion
- VS parameters in standing positions will not be analysed (only provided in individual data listings)
- Frequencies on the ECG clinical interpretation will not be presented (not collected)- Analysis of TEAEs occurrences by MedDRA SOC, PT, seriousness and Treatment Group will be added as per EudraCT requirement

**Note:** the Full Analysis Set definition was clarified with the definition of successful cardioversion as either spontaneous cardioversion before V3 or successful ECV performed at V3.

## 19. DATA PROCESSING

Version 9.4 of SAS Software for windows will be used to perform the statistical procedures.

## 20. APPENDIX

Appendix 1: Conventions related to reference dates and analysis study day variables

- Appendix 2: Cardiovascular safety
- Appendix 3: List of Predefined Potentially Clinically Significant Change for Laboratory Values(⌚)
- Appendix 4: Definition of clinically noteworthy abnormal laboratory values (CNALV)
- Appendix 5: Tables, figures and listings

Appendix 1 CONVENTIONS RELATED TO REFERENCE DATES AND ANALYSIS STUDY DAY VARIABLES	page 1/1
---	-----------------

Reference dates are usually equivalent to:

- For the Reference Start Date: the date of first study drug intake for treated patients, the date of randomisation for randomised and non treated patients and the date of informed consent date in other case (for listings of individual data)
- For the Reference End Date: the date of last intake of study treatment.

Some analysis may require the computation of duration from a reference day to a post-reference day. Duration will be defined as following:

- ⇒ Duration (in days) = Date - Reference date +1 day
- ⇒ Duration (in minutes) = (Date/time) – (Reference date/time)

Appendix 2 CARDIOVASCULAR SAFETY	page 1/1
---	-----------------

**Table 1: Predefined Limits for Potentially Clinically Significant Changes (PSC) and PSC Leading to Clinically Significant Values (PSCV)**

Parameter	PSC	PSCV
SBP	Increase <math>\geq 20</math> mmHg Decrease <math>\geq 20</math> mmHg	SBP <math>\geq 160</math> mmHg and increase <math>\geq 20</math> mmHg SBP <math>\leq 90</math> mmHg and decrease <math>\geq 20</math> mmHg
DBP	Increase <math>\geq 10</math> mmHg Decrease <math>\geq 10</math> mmHg	DBP <math>\geq 100</math> mmHg and increase <math>\geq 10</math> mmHg DBP <math>\leq 50</math> mmHg and decrease <math>\geq 10</math> mmHg
HR	Increase <math>\geq 20</math> bpm Decrease <math>\geq 20</math> bpm	HR <math>\geq 120</math> bpm and increase <math>\geq 20</math> bpm HR <math>\leq 50</math> bpm and decrease <math>\geq 20</math> bpm

**Table 2: Definition of orthostatic hypotension**

Orthostatic Hypotension *
SBP Decrease $\geq 20$ mmHg or DBP Decrease $\geq 10$ mmHg between supine and standing positions

The Consensus Committee of the American Autonomic Society and the American Academy of Neurology. Consensus statement on the definition of orthostatic hypotension, pure autonomic failure and multiple system atrophy. Neurology 1996;46:1470-3.

Appendix 3 LIST OF PREDEFINED POTENTIALLY CLINICALLY SIGNIFICANT CHANGE FOR LABORATORY VALUES(c)	page 1/1
--	-----------------

PARAMETERS	UNIT	PSC	
		Decrease	Increase
MUSCLE	Creatine Phosphokinase	U / l	- 236
KIDNEY	Creatinine	µmol/l	- 35
	Urea	mmol/l	- 3.2
	Uric acid	µmol/l	- 119
	Phosphate	mmol/l	0.39 0.39
	Calcium	mmol/l	0.30 0.30
ELECTROLYTES	Sodium	mmol/l	8 8
	Potassium	mmol/l	1.1 1.1
	Chloride	mmol/l	8 7
	Bicarbonate	mmol/l	7 8
METABOLISM/ NUTRITIONAL	Glucose (random)	mmol/l	3 3.7
	Albumin	g/l	6 6
	Protein	g/l	11 10
	Cholesterol	mmol/l	- 1.97
	HDL cholesterol	mmol/l	0.91 0.85
	LDL cholesterol	mmol/l	2.17 2.04
	Triglycerides	mmol/l	- 2.91
ERYTHROCYTES	Erythrocyte count	T/l	0.7 0.7
	Haemoglobin	g/l	20 -
	Haematocrit	1	0.06 0.06
	MCV	fl	7 7
	MCH (Fe)	fmol	0.19 0.19
	MCHC (Fe)	mmol/l	2 2
LEUKOCYTES	Leukocyte count	G/l	4.2 3.8
DIFFERENTIAL COUNT	Neutrophils	G/l	3.47 3.19
	Lymphocytes	G/l	1.76 1.63
	Monocytes	G/l	- 0.49
	Eosinophils	G/l	- 0.41
	Basophils	G/l	- 0.14
URINE	Specific gravity	-	0.017 0.015
	pH	-	2 2
LIVER	Total bilirubin	µmol/l	- 10
	ASAT (SGOT)	U/l	- N x (23/36)
	ALAT (SGPT)	U/l	- N x (28/45)
	Gamma GT	U/l	- N x (25/38)
	Alkaline phosphatase	U/l	-- N x (30/95)

N = upper limit of normal range

(c) Delta-limits from « Routine Laboratory Tests in Clinical Trials » W. Leigh Thompson, Rocco L. Brunelle, Gregory G. Enas, Patrick J. Simpson and Randy L. Walker Lilly Research Laboratories, Lilly Corporate Center, Indianapolis, Indiana in « Clinical Trials and Tribulations » 1988.

Appendix 4 DEFINITION OF CLINICALLY NOTEWORTHY ABNORMAL LABORATORY VALUES (CNALV)	page 1/1
--	-----------------

PARAMETERS	Baseline value	CNALV
HAEMOGLOBIN	Not missing	Decrease of at least 2g/dl and value < 10 g/dl
	Missing	Value <10g/dl
NEUTROPHILS	-	< 1 500/mm 
WBC (if missing value for neutrophils)	-	< 3 000/mm 
PLATELETS	-	< 100 000/mm 
SERUM CREATININE	Not missing	Increase of at least 30 % as compared to baseline value and value > 150 µmol/l
	Missing	Value > 150 µmol/l
LIVER FUNCTION TESTS		
ALAT	Normal	ALAT > 2 N
	≤ 2.5 N	Increase of at least 100 % as compared to baseline value
	> 2.5 N	value > 5 N
and/or ASAT	Normal	ASAT > 2 N
	≤ 2.5 N	Increase of at least 100 % as compared to baseline value
	> 2.5 N	value > 5 N
and/or Alkaline phosphatase (AP)	Normal	AP > 1.25 N
	Abnormal	AP > 2 N
and/or Total bilirubin (TB)	Normal	TB > 1.5 N
	Abnormal	TB > 2 N

N=upper limit of normal range

*International consensus Meeting. International Journal of Clinical Pharmacology, Therapy and Toxicology, 1990;28:317-322  
Standardisation of definitions and criteria of causality assessment of adverse drug reactions: drugs-induced liver disorders: report of an Standardisation of definitions and criteria of causality assessment of adverse drug reactions: drugs-induced cytopenia.  
Intenational Journal of Clinical Pharmacology, Therapy and Toxicology, 1991;29:75-81*

Appendix 5: TABLES, FIGURES AND LISTINGS		page 1/4
SECTION	Title	RTF reference
10.1	Number of screened and randomised patients, and reasons for non randomisation [Screened patients set]	10_1a_randtrt.RTF
10.1	Number of patients with study discontinuation and reason for discontinuation [Randomised patients set]	10_1d1_pwstudy_ov.RTF
10.2	Number of Patients with Major protocol Deviations [Randomised Patients Set]	10_2a_maj_dev.RTF
10.2	Number of Patients excluded from analysis sets and reasons [Randomised Patients Set]	10_2b_reas_excl.RTF
11.1	Number of patients in each analysis set [Randomised patients Set]	11_1_aset.RTF
11.1	Number of patients by study visit [Randomised patients sets]	11_1b_byvisit.RTF
11.2	Demographic characteristics [FAS]	11_2a_demo.RTF
11.2	Disease characteristics at baseline [FAS]	11_2c_dischar.RTF
11.3	Treatment Compliance [FAS]	11_3a.RTF
11.3	Extrapolated treatment compliance [FAS]	11_3b.RTF
11.4.1.1	Time to first recurrence of AF or atrial emergence - Survival curves and Logrank test [FAS]	11_4_1_1_1_primana_KM.gif
11.4.1.1	Time to first recurrence of AF or atrial emergence - KM summary [FAS]	11_4_1_1_2_primana_KM.RTF
11.4.1.1	Time to first recurrence of AF or atrial emergence - Cox analysis [FAS]	11_4_1_1_3_primana_cox.RTF
11.4.1.1	Time to first recurrence of AF or atrial emergence - Survival curves and Logrank test [PP]	11_4_1_2_1_supana_KM.gif
11.4.1.1	Time to first recurrence of AF or atrial emergence - KM summary [PP]	11_4_1_2_2_supana_KM.RTF
11.4.1.1	Time to first recurrence of AF or atrial emergence - Cox analysis [PP]	11_4_1_2_3_supana_cox.RTF
	Time to first recurrence of AF or atrial emergence - Survival curves and Logrank test [FAS patients with a DHA baseline <= median of the DHA at baseline]	11_4_1_4_1_sensana_DHA1_KM.gif
	Time to first recurrence of AF or atrial emergence - KM summary [FAS patients with a DHA baseline <= median of the DHA at baseline]	11_4_1_4_2_sensana_DHA1_KM.RTF
	Time to first recurrence of AF or atrial emergence - Cox analysis [FAS patients with a DHA baseline <= median of the DHA at baseline]	11_4_1_4_3_sensana_DHA1_cox.RTF
	Time to first recurrence of AF or atrial emergence - Survival curves and Logrank test [FAS patients with a DHA baseline > median of the DHA at baseline]	11_4_1_4_4_sensana_nonDHA2_KM.gif
	Time to first recurrence of AF or atrial emergence - KM summary [FAS patients with a DHA baseline > median of the DHA at baseline]	11_4_1_4_5_sensana_DHA2_KM.RTF
	Time to first recurrence of AF or atrial emergence - Cox analysis [FAS patients with a DHA baseline > median of the DHA at baseline]	11_4_1_4_6_sensana_DHA2_cox.RTF

SECTION	Title	RTF reference
	Time to first recurrence of AF or atrial emergence - Survival curves and Logrank test [FAS patients with vascular or cardiac therapeutic procedures that will be identified in the data review meeting report<3months]	11_4_1_5_1_sensana_surg1_KM.gif
	Time to first recurrence of AF or atrial emergence - KM summary [FAS patients with vascular or cardiac therapeutic procedures that will be identified in the data review meeting report<3months]	11_4_1_5_2_sensana_surg1_KM.RTF
	Time to first recurrence of AF or atrial emergence - Cox analysis [FAS patients with vascular or cardiac therapeutic procedures that will be identified in the data review meeting report<3months]	11_4_1_5_3_sensana_surg1_cox.RTF
	Time to first recurrence of AF or atrial emergence - Survival curves and Logrank test [FAS patients without vascular or cardiac therapeutic procedures that will be identified in the data review meeting report<3months]	11_4_1_5_4_sensana_surg2_KM.gif
	Time to first recurrence of AF or atrial emergence - KM summary [FAS patients without vascular or cardiac therapeutic procedures that will be identified in the data review meeting report<3months]	11_4_1_5_5_sensana_surg2_KM.RTF
	Time to first recurrence of AF or atrial emergence - Cox analysis [FAS patients without vascular or cardiac therapeutic procedures that will be identified in the data review meeting report<3months]	11_4_1_5_6_sensana_surg2_cox.RTF
11.4.1.1	Primary criterion - Time to first recurrence of AF or atrial emergence and interaction treatment group by country– Cox analysis [FAS]	11_4_1_5_1_inter_country.RTF
11.4.1.1	Primary criterion - Time to first recurrence of AF or atrial emergence and interaction treatment group by DHA baseline – Cox analysis [FAS]	11_4_1_6_1_inter_DHA.RTF
11.4.1.1	Primary criterion - Time to first recurrence of AF or atrial emergence and gender – Cox analysis [FAS]	11_4_1_7_1_gender.RTF
11.4.1.1	Primary criterion - Time to first recurrence of AF or atrial emergence and age – Cox analysis [FAS]	11_4_1_8_1_age.RTF
11.4.1.1	Primary criterion - Time to first recurrence of AF or atrial emergence and BSA – Cox analysis [FAS]	11_4_1_9_1_BSA.RTF
11.4.1.1	Primary criterion - Time to first recurrence of AF or atrial emergence and duration of current AF up to selection visit – Cox analysis [FAS]	11_4_1_10_1_current.RTF
11.4.1.1	Primary criterion - Time to first recurrence of AF or atrial emergence and time from first documented persistent AF up to selection visit– Cox analysis [FAS]	11_4_1_11_1_firstFA.RTF
11.4.1.1	Primary criterion - Time to first recurrence of AF or atrial emergence and Time from heart failure diagnosis up to selection visit – Cox analysis [FAS]	11_4_1_12_1_heartfail.RTF
11.4.1.1	Primary criterion - Time to first recurrence of AF or atrial emergence and NYHA grade – Cox analysis [FAS]	11_4_1_13_1_NYHA.RTF
11.4.1.1	Primary criterion - Time to first recurrence of AF or atrial emergence and left atrial area – Cox analysis [FAS]	11_4_1_14_1_leftatrial.RTF
11.4.1.1	Primary criterion - Time to first recurrence of AF or atrial emergence and Left ventricular ejection fraction – Cox analysis [FAS]	11_4_1_15_1_leftventri.RTF

SECTION	Title	RTF reference
11.4.1.2	Number of AF/flutter episodes in the first week following V3[FAS]	11_4_1_2_1_nbAF.RTF
11.4.1.2	Duration of AF/flutter episodes in the first week following V3[FAS]	11_4_1_2_2_durAF.RTF
11.4.1.2	Time to first AF recurrence /flutter emergence less than 10 minutes - Survival curves and Logrank test [FAS]	11_4_1_2_4_1_AFless10_KM.gif
11.4.1.2	Time to first AF recurrence /flutter emergence less than 10 minutes - KM summary [FAS]	11_4_1_2_4_2_AFless10_KM.RTF
11.4.1.2	Time to first AF recurrence/flutter emergence less than 10 minutes - Cox analysis [FAS]	11_4_1_2_4_3_AFless10_cox.RTF
11.4.1.2	Time to first symptomatic AF/Flutter - Survival curves and Logrank test [FAS]	11_4_1_2_4_1_symptAF_KM.gif
11.4.1.2	Time to first symptomatic AF/Flutter - KM summary [FAS]	11_4_1_2_4_2_symptAF_KM.RTF
11.4.1.2	Time to first symptomatic AF/Flutter - Cox analysis [FAS]	11_4_1_2_4_3_symptAF_cox.RTF
11.4.1.2	Maximum EHRA score- CMH [FAS]	11_4_1_2_5_ehra.RTF
11.4.1.2	Frequency of symptoms - -[FAS]	11_4_1_2_6_symptfreq.RTF
11.4.1.2	Presumed arrhythmia - -[FAS]	11_4_1_2_7_arrhy.RTF
11.4.1.2	Number of symptomatic AF recurrence/Flutter emergence - [FAS]	11_4_1_2_8_nb_symptrecu.RTF
11.4.1.2	Number of hospitalizations- [FAS]	11_4_1_2_9_1_nb_hospit.RTF
11.4.1.2	Duration of hospitalizations- [FAS]	11_4_1_2_9_2_dur_hospit.RTF
11.4.1.2	Cardioversion assessment- [FAS]	11_4_1_2_10_cardiov_asses.RTF
11.4.1.2	Echocardiographic parameters values and changes over time- [FAS]	11_4_1_2_11_echoparam_assess.RTF
11.4.1.2	Values and changes from baseline for red blood cell concentration of DHA [FAS]	11_4_1_2_12_DHA.RTF
12.1	Total extent of exposure to the study drug [Safety Set]	12_1_a_expos.RTF
12.2.1	Summary of adverse events [Safety Set]	12_2_1_ae_overview.RTF
12.2.2	Number of patients with at least one treatment-emergent adverse event by MedDRA primary system organ class and preferred term [Safety Set]	12_2_2a_tae_socpt.RTF
12.2.2	Number of patients with at least one related treatment-emergent adverse event by MedDRA primary system organ class and preferred term [Safety Set]	12_2_2b_relteae_socpt.RTF
12.3.1.1	Listing of deaths [Safety Set]	12_3_1_1_deaths_list.rtf
12.3.1.2	Listing of serious adverse events [Safety Set]	12_3_1_2_sae_list.rtf
12.3.1.3	Listing of adverse events leading to definitive study treatment discontinuation [Safety Set]	12_3_1_3_aedefstoprt_list.rtf
12.4.2.2	Hematology: Number of patients with variations over time [Safety Set]	12_4_2_2_1Hem.RTF

SECTION	Title	RTF reference
12.4.2.2	Biochemistry: Number of patients with variations over time [Safety Set]	12_4_2_2_1Bioch.RTF
12.4.2.3	CNALV: Patients with haemoglobin < 10 g/dL and decreased from baseline >=2 g/dL (if baseline was measured) [Safety Set]	12_4_2_3a_hemog.RTF
12.4.2.3	CNALV: Patients with neutrophils < 1.5 G/L or WBC < 3G/L (if neutrophils missing) [Safety Set]	12_4_2_3b_neutr.RTF
12.4.2.3	CNALV: Patients with platelets < 100 G/L [Safety Set]	12_4_2_3c_plat.RTF
12.4.2.3	CNALV: Patients with ALAT > 2N or ASAT > 2N or ALP > 1.25N or TB > 1.5N, and normal baseline value, or GGT > 3 N (if baseline<3N) [Safety Set]	12_4_2_3d_liver.RTF
12.4.2.3	CNALV: Patients with creatinine > 150 µmol/L and increase by 30% from baseline value (if any) [Safety Set]	12_4_2_3e_creat.RTF
12.4.2.3	Patients with estimated creatinine clearance < 30 ml/min [Safety Set]	12_4_2_3f_clear.RTF
12.5.1	SBP Changes over Time [Safety Set]	12_5_1_1_figCH_SBP.gif
12.5.1	DBP Changes over Time [Safety Set]	12_5_1_1_figCH_DBP.gif
12.5.1	HR Changes over Time [Safety Set]	12_5_1_1_figCH_HR.gif
12.5.1	Supine VS measurements : Incidence of post-baseline PSCs and PSCVs [Safety Set]	12_5_1_2_SCVS.RTF
12.5.1	Supine BP measurements : Incidence of post-baseline PSCs and PSCVs [Safety Set]	12_5_1_2_SCBP.RTF
12.5.1	Supine HR measurements : Incidence of post-baseline PSCs and PSCVs [Safety Set]	12_5_1_2_SCHR.RTF
12.5.1	BP measurements : Number of patients with at least one post-baseline orthostatic hypotension [Safety Set]	12_5_1_2_OrthoBP.RTF
12.5.3	Patients with ECG abnormalities (Investigator's evaluation) [Safety Set]	12_5_3_1_2_ecg_abn.RTF
14.1	Number of patients per country and centre [Randomised patients]	14_1a_asetpercenter_all.RTF
14.1	Number of patients with minor deviations [Randomised Patients Set]	14_1b_minor_dev.RTF
14.1	Demographic characteristics [Safety Set]	14_1c_demoSaf.RTF
14.1	Demographic characteristics [PP]	14_1c_demoPP.RTF
14.1	Disease characteristics at baseline [PP]	14_1c_discharPP.RTF
14.1	Number (%) of patients with at least one medical or surgical history by MedDRA primary system organ class and preferred term [Safety Set]	14_1d_medhist_socpt_saf.RTF
14.1	Number (%) of patients with at least one concomitant disease at time of selection by MedDRA primary system organ class and preferred term [Safety Set]	14_1e_cdiseasesel_socpt_saf.RTF
14.1	Number (%) of patients with at least one medication taken before first study drug administration, by WHO-Drug ATC1and ATC2 [Safety Set]	14_1f_pmed_atc_saf.RTF
14.1	Number (%) of patients with at least one medication before first study treatment administration linked to the study pathology, by WHO-Drug ATC1and ATC2 [Safety Set]	14_1g_pmed_link_atc_saf.RTF
14.3.1	Number of patients with at least one AE occurred before first administration by MedDRA primary system organ class and preferred term [Safety Set]	14_3_1_ae_socpt.RTF
14.3.1	Number of patients with at least one treatment-emergent adverse event by MedDRA primary system organ class, preferred term and maximum intensity [Safety Set]	14_3_1a_tae_socptmaxi.RTF

SECTION	Title	RTF reference
14.3.1	Number of patients with at least one treatment-emergent adverse event by MedDRA primary system organ class, preferred term and most severe relationship to study drug [Safety Set]	14_3_1b_tae_socptmaxr.RTF
14.3.1	Number of patients with at least one non serious TEAE, and the number of associated occurrences, by MedDRA primary system organ class and preferred term [Safety Set]	14_3_1c_nsaeteae_socpt.RTF
14.3.1	Number of patients with at least one TEAE, and the number of occurrences of TEAEs by MedDRA SOC, Preferred Term, seriousness and Treatment Group [Safety Set]	14_3_1e_tae_occu_socpt.RTF
14.3.1	Number of patients with at least one related TEAE, and the number of occurrences of related TEAEs by MedDRA SOC, Preferred Term, seriousness and Treatment Group [Safety Set]	14_3_1f_relteae_occu_socpt.RTF
14.3.4	Hematology Values and changes over time [Safety Set]	14_3_4_1a_1Hem.RTF
14.3.4	Biochemistry Values and changes over time [Safety Set]	14_3_4_1a_2Bioch.RTF
14.3.4	Coagulation Values and changes over time [Safety Set]	14_3_4_1a_3Coag.RTF
14.3.4	Hematology Changes of values relative to normal ranges over time [Safety Set]	14_3_4_1c_1Hem.RTF
14.3.4	Biochemistry Changes of values relative to normal ranges over time [Safety Set]	14_3_4_1c_2Bioch.RTF
14.3.4	Lab scatter plot: haematocrit(Week 4) [Safety Set]	14_3_4_2hema_w4.gif
14.3.4	Lab scatter plot: haemoglobin (Week 4) [Safety Set]	14_3_4_2hemog_w4.gif
14.3.4	Lab scatter plot: RBC count (Week 4) [Safety Set]	14_3_4_2RBC_w4.gif
14.3.4	Lab scatter plot: WBC count (Week 4) [Safety Set]	14_3_4_2WBC_w4.gif
14.3.4	Lab scatter plot: reticulocytes (Week 4) [Safety Set]	14_3_4_2retic_w4.gif
14.3.4	Lab scatter plot: Platelets (Week 4) [Safety Set]	14_3_4_2plat_w4.gif
14.3.4	Lab scatter plot: haematocrit(Week 12) [Safety Set]	14_3_4_2hema_w12.gif
14.3.4	Lab scatter plot: haemoglobin (Week 12) [Safety Set]	14_3_4_2hemog_w12.gif
14.3.4	Lab scatter plot: RBC count (Week 12) [Safety Set]	14_3_4_2RBC_w12.gif
14.3.4	Lab scatter plot: WBC count (Week 12) [Safety Set]	14_3_4_2WBC_w12.gif
14.3.4	Lab scatter plot: reticulocytes (Week 12) [Safety Set]	14_3_4_2retic_w12.gif
14.3.4	Lab scatter plot: Platelets (Week 12) [Safety Set]	14_3_4_2plat_w12.gif
14.3.4	Lab scatter plot: haematocrit(Week 24) [Safety Set]	14_3_4_2hema_w24.gif
14.3.4	Lab scatter plot: haemoglobin (Week 24) [Safety Set]	14_3_4_2hemog_w24.gif
14.3.4	Lab scatter plot: RBC count (Week 24) [Safety Set]	14_3_4_2RBC_w24.gif
14.3.4	Lab scatter plot: WBC count (Week 24) [Safety Set]	14_3_4_2WBC_w24.gif
14.3.4	Lab scatter plot: reticulocytes (Week 24) [Safety Set]	14_3_4_2retic_w24.gif
14.3.4	Lab scatter plot: Platelets (Week 24) [Safety Set]	14_3_4_2plat_w24.gif
14.3.4	Lab scatter plot: ASAT (last value) [Safety Set]	14_3_4_2AST.gif
14.3.4	Lab scatter plot: ALAT (last value) [Safety Set]	14_3_4_2ALT.gif

SECTION	Title	RTF reference
14.3.4	Lab scatter plot: Alkaline phosphatase (last value) [Safety Set]	14_3_4_2Alkaline_phos.tif
14.3.4	Lab scatter plot: Conjugated bilirubin (last value) [Safety Set]	14_3_4_2Conjugated_Bili.tif
14.3.4	Lab scatter plot: Total bilirubin (last value) [Safety Set]	14_3_4_2Total_Bili.tif
14.3.4	Lab scatter plot: Gamma GT (last value) [Safety Set]	14_3_4_2GGT.tif
14.3.4	Lab scatter plot: Total Cholesterol (last value) [Safety Set]	14_3_4_2Total_Chol.tif
14.3.4	Lab scatter plot: HDL Cholesterol (last value) [Safety Set]	14_3_4_2HDL_Chol.tif
14.3.4	Lab scatter plot: LDL Cholesterol (last value) [Safety Set]	14_3_4_2LDL_Chol.tif
14.3.4	Lab scatter plot: Sodium (last value) [Safety Set]	14_3_4_2Sod.tif
14.3.4	Lab scatter plot: Potassium (last value) [Safety Set]	14_3_4_2Pota.tif
14.3.4	Lab scatter plot: Bicarbonate (last value) [Safety Set]	14_3_4_2Bicar.tif
14.3.4	Lab scatter plot: Chloride (last value) [Safety Set]	14_3_4_2Chlo.tif
14.3.4	Lab scatter plot: Albumin (last value) [Safety Set]	14_3_4_2Albu.tif
14.3.4	Lab scatter plot: Creatinine (last value) [Safety Set]	14_3_4_2Creat.tif
14.3.4	Lab scatter plot: Fasting glucose (last value) [Safety Set]	14_3_4_2Gluc.tif
14.3.4	Lab scatter plot: Triglycerides (last value) [Safety Set]	14_3_4_2Trig.tif
14.3.4	Lab scatter plot: Fibrinogen (last value) [Safety Set]	14_3_4_2Fibri.tif
14.3.4	Lab scatter plot: prothrombin time/INR (last value) [Safety Set]	14_3_4_2coag1.tif
14.3.4	Lab scatter plot: Activated partial thromboplastin time (last value) [Safety Set]	14_3_4_2coag2.tif
14.3.4	Lab scatter plot: Thrombin clotting time (last value) [Safety Set]	14_3_4_2coag3.tif
14.3.5	Supine Systolic Blood Pressure Measurements Over Time [Safety Set]	14_3_5_1_sbp.GIF
14.3.5	Supine Diastolic Blood Pressure Measurements Over Time [Safety Set]	14_3_5_1_dbp.GIF
14.3.5	Supine Blood Pressure Measurements Over Time [Safety Set]	14_3_5_1_BP.RTF
14.3.5	Supine Heart Rate Measurements Over Time [Safety Set]	14_3_5_1_hr.GIF
14.3.5	Supine Heart Rate Measurements Over Time [Safety Set]	14_3_5_1_hr.RTF
14.3.5	Number of patients with Predefined Potentially Clinically Significant Change (PSC) and with PSC Leading to Clinically Significant Value (PSCV) in supine Systolic Blood Pressure [Safety Set]	14_3_5_1b_PSC_PSCV_sbp.RTF
14.3.5	Number(%) of patients with Predefined Potentially Clinically Significant Change (PSC) and with PSC Leading to Clinically Significant Value (PSCV) in supine Diastolic Blood Pressure [Safety Set]	14_3_5_1b_PSC_PSCV_dbp.RTF
14.3.5	Number(%) of patients with Predefined Potentially Clinically Significant Change (PSC) and with PSC Leading to Clinically Significant Value (PSCV) in supine Heart Rate [Safety Set]	14_3_5_1b_PSC_PSCV_hr.RTF
14.3.5	Body weight values and changes from baseline over time [Safety Set]	14_3_5_2_1_bodyw.RTF
14.3.5	Number (%) of patients with at least one concomitant medication, by WHO-Drug ATC1 and ATC2 [Safety Set]	14_3_5_5_1_cmed_atc.RTF
16.1.7	16.1.7: Randomisation	16_1_7.RTF
16.2.1	16.2.1: Discontinued patients	16_2_1.RTF

SECTION	Title	RTF reference
16.2.2	16.2.2: Protocol deviations for randomised patients	16_2_2.RTF
16.2.3	16.2.3: Reasons for exclusion from analysis sets	16_2_3.RTF
16.2.4.1	16.2.4.1: Demographic data	16_2_4_1.RTF
16.2.4.2	16.2.4.2: Disease characteristics	16_2_4_2.RTF
16.2.4.3	16.2.4.3: Medical and Surgical History by patient	16_2_4_3.RTF
16.2.4.4	16.2.4.4: Concomitant Diseases by patient	16_2_4_4.RTF
16.2.4.5	16.2.4.5.1 Prior medications by Patient	16_2_4_5_1.RTF
16.2.4.5	16.2.4.5.2 Prior medications by ATC classification	16_2_4_5_2.RTF
16.2.4.6	16.2.4.6 Inclusion and non-inclusion criteria	16_2_4_6.RTF
16.2.5.1	16.2.5.1: Dates of Visit	16_2_5_1.RTF
16.2.5.2	16.2.5.2: Global Compliance	16_2_5_2.RTF
16.2.5.3	16.2.5.3 Exposure for randomised patients	16_2_5_3.RTF
16.2.6.1	16.2.6.1: Time to first recurrence of AF or atrial flutter	16_2_6_1.RTF
16.2.6.2	16.2.6.2: Holter measurements	16_2_6_2.RTF
16.2.6.3	16.2.6.3: TTTEM measurements	16_2_6_3.RTF
16.2.6.4	16.2.6.4: DHA measurements	16_2_6_4.RTF
16.2.7.1	16.2.7.1: Adverse Events Reported Term, Preferred Term and Dates	16_2_7_1.RTF
16.2.7.2	16.2.7.2: Adverse Events by Patient	16_2_7_2.RTF
16.2.7.3	16.2.7.3: Adverse Events by SOC, PT, LLT	16_2_7_3.RTF
16.2.8.1	16.2.8.1: Listing of individual laboratory measurements	16_2_8_1.RTF
16.2.8.2	16.2.8.2: Listing of individual coagulation parameters measurements	16_2_8_2.RTF
16.2.9.1	16.2.9.1: Listing of vital signs measurements	16_2_9_1.RTF
16.2.9.2	16.2.9.2: ECG measurements	16_2_9_2.RTF
16.2.9.3	16.2.9.3: Physical examination	16_2_9_3.RTF
16.2.10.1	16.2.10.1: Concomitant medications by Patient	16_2_10_1.RTF
16.2.10.2	16.2.10.2: Concomitant medications by ATC classification	16_2_10_2.RTF

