### 17.4. LABORATORY DATA

Clinically noteworthy abnormal laboratory values (CNALV) (See Appendix 4) will be identified and described on an individual basis. Five separate individual data listings by treatment group will be provided:

- for haemoglobin (including corresponding individual results of erythrocytes and haematocrit),
- for platelets (including corresponding individual results of erythrocytes and leucocytes),
- for liver function parameters (including corresponding individual results of gamma-GT),

- for neutrophils or leucocytes (including corresponding individual results of basophils, eosinophils, lymphocytes and monocytes)
- for serum creatinine

Estimated creatinine clearance (ml/min) will be calculated using Cockcroft and Gault method as

$$\frac{[140 - \text{age (in years)}] \times \text{body weight (in kg)}}{\text{serum creatinine (in } \mu\text{mol/L}) \times 0.814} \times (0.85 \text{ for female})$$

Patients with estimated creatinine clearance (Cockcroft method)  $< 30$  ml/min will be also described on an individual basis. Values of estimated creatinine clearance (Cockcroft method) will be classified as following:

Creatinine clearance categories (ml/min)
<15
[15-30[

For each laboratory parameter, values and changes from baseline will be tabulated by treatment group and assessment time.

For all biochemistry parameters, scatter plots highlighting individual results will display the baseline and last value of the laboratory measurements for each patient by locating the point defined by the baseline value on the abscissa and respectively last value in the ordinate.

For all haematology parameters, scatter plots highlighting individual results will display the baseline and week 4, week 12 and week 24 of the laboratory measurements for each patient by locating the point defined by the baseline value on the abscissa and respectively week 4, week 12 and week 24 value in the ordinate.

Each treatment group will be differently identified. The first bisecting line ( $45^\circ$  line), the lines of lower and upper normal range, the lines of Potentially Clinically Significant Change (PSC) range and Clinically noteworthy abnormal laboratory value (CNALV) range added on the plots (see Appendices 3 and 4).

For all blood laboratory parameters, shift tables will be provided to depict the numbers of patients with post-trial drug administration variations at each assessment time as compared to the baseline

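### The Appendix 5 title of the liver CNALV listing states a selection rule that differs from the Appendix 4 definition named in Section 17.4

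*SAP*

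**What the plan says.** Three places in the SAP bear on the liver listing.

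- **Section 17.4** sets the general rule: "Clinically noteworthy abnormal laboratory values (CNALV) (See Appendix 4) will be identified and described on an individual basis". It then names five listings, one of them "for liver function parameters (including corresponding individual results of gamma-GT". Gamma-GT is thus shown beside the liver results and does not select patients.
- **Appendix 4** makes the liver rule depend on baseline. ALAT and ASAT each have three rows: above 2 N from a normal baseline; "Increase of at least 100 % as compared to baseline value" from a baseline up to 2.5 N; and above 5 N from a baseline over 2.5 N. Alkaline phosphatase must exceed 1.25 N from a normal baseline or 2 N from an abnormal one. Total bilirubin must exceed 1.5 N or 2 N in the same way. There is no gamma-GT row.
- **Appendix 5**, in the 12.4.2.3 entry for output 12_4_2_3d_liver, gives the title "CNALV: Patients with ALAT > 2N or ASAT > 2N or ALP > 1.25N or TB > 1.5N, and normal baseline value", continued by "or GGT > 3 N (if baseline<3N".

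**The concern.** The title and the definition select different patients for what is meant to be the same listing. The title is narrower for ALAT, ASAT, alkaline phosphatase and bilirubin, because only the normal-baseline thresholds remain. It is wider for gamma-GT. Two programmers, one working from Section 17.4 and one from the output list, could both claim to follow the SAP and still produce different liver listings.

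What is at stake is the individual flagging of liver abnormalities in patients whose test was already raised at baseline. Safety and tolerability are a secondary objective, and the CNALV listing is where such cases are identified one by one.

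**Working it through.** The SAP states no figure to reproduce, so the check codes both rules as written and compares them. Values are multiples of the upper limit of normal, N. A normal baseline is taken as at most 1 N. The baseline condition in the title is read separately for each parameter.

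**Rules for baseline b and post-baseline value v**

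| Parameter | Appendix 4 | Appendix 5 title |
|---|---|---|
| ALAT, ASAT | b ≤ 1: v > 2; 1 < b ≤ 2.5: v ≥ 2b; b > 2.5: v > 5 | b ≤ 1 and v > 2 |
| Alkaline phosphatase | b ≤ 1: v > 1.25; b > 1: v > 2 | b ≤ 1 and v > 1.25 |
| Total bilirubin | b ≤ 1: v > 1.5; b > 1: v > 2 | b ≤ 1 and v > 1.5 |
| Gamma-GT | no rule | b < 3 and v > 3 |

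**Test cases (gamma-GT aside)**

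| Parameter | b to v | Appendix 4 | Title |
|---|---|---|---|
| ALAT/ASAT | 0.8 to 2.1 N | flagged | flagged |
| ALAT/ASAT | 1.5 to 3.0 N | flagged | not flagged |
| ALAT/ASAT | 2.4 to 6 N | flagged | not flagged |
| ALAT/ASAT | 2.6 to 5.1 N | flagged | not flagged |
| ALAT/ASAT | 3 to 10 N | flagged | not flagged |
| Alkaline phosphatase | 0.9 to 1.3 N | flagged | flagged |
| Alkaline phosphatase | 1.1 to 2.1 N | flagged | not flagged |
| Total bilirubin | 0.9 to 1.6 N | flagged | flagged |
| Total bilirubin | 1.2 to 2.1 N | flagged | not flagged |

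**Grid for ALAT/ASAT.** Both b and v ran from 0.05 N to 12 N in steps of 0.05 N. No pair was flagged by the title alone. Every pair flagged by Appendix 4 alone had a baseline above 1 N; the lowest was 1.05 N. The two rules agree at normal baselines and part only at abnormal ones. The grid shows where they part, not how often patients fall there.

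**Example in units, assuming N = 45 U/l for illustration.** ALAT goes from 50 to 220 U/l. Then 50/45 = 1.1 N and 220/45 = 4.9 N, and the increase is (220 − 50)/50 = 340%, above the 100% limit. Appendix 4 flags it. The ALAT part of the title does not, because 50 exceeds 45. The patient is left off the listing only if ASAT, alkaline phosphatase, bilirubin and gamma-GT also fail to qualify under the title.

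**The other direction.** A patient whose only finding is gamma-GT above 3 N, from a baseline below 3 N, is a CNALV under the title but not under Appendix 4.

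**Comparison with the other CNALV titles.** Haemoglobin ("CNALV: Patients with haemoglobin < 10 g/dL and decreased from baseline >=2 g/dL (if baseline was measured") and creatinine ("CNALV: Patients with creatinine > 150 µmol/L and increase by 30% from baseline value (if any") both carry over the Appendix 4 rule, including the missing-baseline case. The neutrophil, white-cell and platelet limits agree after unit conversion: 1 500/mm³ = 1.5 G/L, 3 000/mm³ = 3 G/L and 100 000/mm³ = 100 G/L. The liver title is the only one of the five that departs.

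**The case against.** The strongest reply is that the SAP already settles which rule governs. Section 17.4 points to Appendix 4, while Appendix 5 is an index of titles and file names, and nothing says that selection rules are taken from titles. Its titles are loose elsewhere: several refer to atrial emergence where flutter emergence is meant, and the procedure-subgroup titles keep a three-month limit that Section 14.1.4 does not have. This stands in part. It makes the omission conditional on a program that follows the title. It does not make the title harmless shorthand, because the other CNALV titles reproduce their definitions with the conditional cases, and the gamma-GT clause has a threshold and a baseline condition of its own.

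A second reply is that the data stay visible. Biochemistry scatter plots show each patient's baseline against the last value with CNALV lines, changes from baseline are tabulated, and all laboratory values are listed. The flow-chart schedules biochemistry only at V1 and V9, so the last value normally is the scheduled post-baseline one. This also stands: what could be lost is the flag, not the data. The cover is incomplete, though. The shift tables use a low/normal/high scale, so 1.1 N to 4.9 N appears as high to high. A peak at an unscheduled visit that later resolves would not be the last value plotted, although Section 10.2 counts unscheduled measurements when detecting individual abnormalities.

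A reader might infer that the listing excludes every patient with an abnormal baseline. The title does not support that. Its criteria are joined by 'or', so on the per-parameter reading a patient with raised baseline ALAT can still enter through another test that was normal at baseline. The gamma-GT arm admits any gamma-GT baseline below 3 N. A reader might also suppose that raised baseline liver tests are frequent in this population, but the SAP gives no baseline liver data.

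**Conclusion.** The inconsistency is real and lies in the current text; neither the versioning table nor Section 18 explains it. The title omits the Appendix 4 rules for abnormal baselines and adds a gamma-GT criterion that Appendix 4 lacks and Section 17.4 treats as accompanying data.

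The consequence is limited. If the program follows the title, the patients not flagged are those whose only qualifying parameter was abnormal at baseline and who do not meet the gamma-GT arm. This rests on reading the baseline condition per parameter. The number affected cannot be derived from the SAP. The gamma-GT clause can only add patients to the listing. The safety analysis is descriptive, and the primary analysis and the analysis sets are unaffected. The point is worth correcting before programming because it concerns the individual detection of liver abnormalities and is cheap to settle.

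**What to change.** Reconcile Section 17.4, Appendix 4 and Appendix 5 before the listing is programmed:

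- Retitle output 12_4_2_3d_liver as liver CNALV as defined in Appendix 4, and program all its rows, including those for abnormal baselines.
- Decide once whether gamma-GT is a selection criterion or is only displayed, and say so in all three places. If it selects, Appendix 4 needs a gamma-GT row and Section 17.4 needs matching wording. If it is only displayed, remove the clause from the title.

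The cost is one title and its program, a line of text wherever the gamma-GT decision requires it, and a slightly longer descriptive listing. No new data are needed.
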